6.2 Sample Size

Sample Size Determination is based on our pilot studies of overnight CLC. We conservatively estimate that the effect size of USS+SAP(d) vs. SAP will be $f \ge 0.2$. Power calculations (G*Power 3) assuming $\alpha = 0.01$, 90% power, correlation of 0.4 between the repeated measures, and attrition of up to 31% yield a sample size of **N=110** subjects to be randomized at baseline, with N=76 subjects completing the study. For SA2 using USS+CLC(d), our pilot data with this same system during the day indicate a larger effect size f=0.3. For SA-3, the expected effect size is f=0.35-0.4 based on our previous interviews. Thus, a sample size that is adequate for SA-1 will have adequate power to address SA-2 and SA-3 as well.

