1.5 Protocol Overview

1.5.1 Sample Size

Up to 110 adult subjects age \geq 18 to <70 years old will be enrolled so that approximately 76 subjects complete the entire study at University of Virginia, allowing for up to 31% attrition rate due to the duration of the study protocol).

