2.1 Study Population

We anticipate recruiting up to 110 subjects, ages ≥18 and <70 years. An equal number of males and females will be recruited, and all racial/ethnic groups will be eligible for participation. Based on our experience, we expect that approximately 76% in each arm will complete the study (N=64) and has been increased to account for inclusion of new devices. The randomization will aim to balance the age/gender distributions of the participants in the two groups and to match the groups by baseline HbA1c.

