The subject must be able to complete system-related tasks independently to be eligible to continue in the study.

3.6 Visit 5 - AP System Run-In phase: Home Use in Pump Only (Open Loop) Configuration

Eligible subjects who have not had recent use of the system (more than ~2 weeks of use in the past 6 months or more than ~2 months of use in the past year) will complete up to 2-week home use period with the full system in pump only (open loop) configuration where no closed loop algorithms are activated. Subject will be instructed not to start closed loop during this run-in phase. Subjects who have had prior experience with the AP system as defined above will not be required to do Visit 5. Subjects who are demonstrating proficiency, as determined by the study physician, may have a shorter open loop run-in phase with a minimum of 5 days duration Criteria for proficiency is listed in section 3.11.

For the inControl system, remote monitoring will be available during this period for the purposes of data collection and ad hoc assessment of system performance by study team. The study team will be available for the subject to contact during this phase. Study staff will contact the subject and review data on the Remote Monitoring once daily. The subject may contact the study staff at any time.

For the Tandem-G6 system, remote monitoring will not be available. Study staff will contact the subject daily to assess difficulties with the use of the system. The subject may contact the study staff at any time. If the study team requires additional information, the subject may be asked to upload the pump at home so that the study can review data on the t:connect website.

3.7 Visit 6 + Visit 7 + Visit 8 Washout Following Completion of the Each Study Phase

At the completion of the each phase of the study, subjects will have up to a two week washout prior to proceeding to the next phase.

First Phase: Group A 8 weeks of SAP; Group B 8 weeks of USS +SAP(d) Second Phase: Group A 8 weeks of USS +SAP(d); Group B 8 weeks of USS + CLC(d) Third Phase: Group A 8 weeks of USS + CLC(d); Group B 8 weeks of USS +SAP (d) Fourth Phase: Group A 8 weeks of USS + SAP(d); Group B 8 weeks of SAP

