6.1 Analysis Plan

Statistical Analysis: The overall analysis will follow Intention-to-treat approach and will use Generalized Linear Mixed Models (e.g. those available in IBM SPSS) including fixed factors following the factorial designs presented in study figure for the specific aims listed below, and random effects reflecting patients' attrition rate.

Metrics:

- (i) Five HbA1c determinations approximately 10 weeks apart;
- (ii) Eight-week sequences of CGM data accompanied by BG self-monitoring readings and recording of the timing of events such as meals and exercise through the GUI
- (iii) Psychometric questionnaires administered concurrently with HbA1c, and
- (iv) Individual structured interview and qualitative/quantitative technology acceptance assessments. CGM data will be used to compute established metrics of risk for hypoglycemia, e.g. the Low BG Index (LBGI), glucose variability, and BG dynamics, as presented in our review of statistical tools for CGM data analysis.

Primary Hypothesis by Specific Aims of the Study

Specific Aim 1: Overnight CLC achieved by USS+SAP(d) will be superior to SAP alone in terms of: (1) Improved HbA1c without increasing the risk for hypoglycemia; (2) Reduced incidence and risk for hypoglycemia overnight, and (3) Reduced fear of hypoglycemia and improved diabetes quality of life scores.

Specific Aim 2: CLC during the day achieved by USS+CLC(d) will preserve the benefits of USS+SAP(d) and will be superior to USS+SAP(d) in terms of: (1) Increased time within target range of 70-180mg/dl during the day; (2) Reduced risk for hypoglycemia during and after exercise, and (3) Reduced postprandial glucose variability.

Specific Aim 3: CLC system acceptance evaluated by an individual structured and technology acceptance scores will be: (1) Superior, for USS+SAP(d) compared to SAP alone, i.e. adding USS overnight will increase patients' acceptance of CLC, and (2) Marginally inferior, for USS+CLC(d) compared to USS+SAP(d); i.e. some patients would prefer SAP alone during the day due to perceived increased system complexity.

Primary Outcomes

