Specific Aim 1: The **primary outcome** is improvement in diabetes control on USS+SAP(d) vs. SAP alone as defined by reduced risk for hypoglycemia (Time <70 mg/dL by CGM) without increase in HbA1c. Repeated Measures ANOVA with covariate will assess this effect. Inversely, comparing HbA1c with covariate overnight Time <70 mg/dL by CGM will address SA1-2, while comparing the psychometric questionnaire scores pre-post treatment will address SA1-3.

Specific Aim 2: The **primary outcome** is improved time within the target range of 70-180mg/dl during the day on USS+ CLC(d) vs. USS+SAP(d). Repeated Measures ANOVA following the study design outlined will assess this effect. SA2-2 will be addressed

comparing frequency of hypoglycemia within the post-exercise periods recorded by the system; SA2-3 will be addressed using Variability-Grid Analysis, and SA-4 will be addressed by a sub-analysis limited to those who did not achieve HBA1c≤7.5% during the first 3 months of the study.

Specific Aim 3: will be addressed by comparing structured interviews and technology acceptance scores along the two sequences of treatment modalities specified in the study design: treatment escalation for Group A and de-escalation for Group B. Analyzing the random effect of patient attrition will shed additional light on system acceptance.

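### The 90% power in Section 6.2 is not the power for USS+SAP(d) vs SAP: the stated inputs give about 70–72% with 76 completers, or about 85% with both USS+SAP(d) phases pooled and no period effects

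*Combined protocol and SAP*

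**What the plan says.** Section 6.2 ties the effect size to one pair of modalities: "We conservatively estimate that the effect size of USS+SAP(d) vs. SAP will be" at least f = 0.2. With alpha = 0.01 in G*Power, it says that "90% power, correlation of 0.4 between the repeated measures, and attrition of up to 31% yield a sample size of" 110 randomized and 76 completing. It then argues that a size adequate for Specific Aim 1 (SA1) is adequate for Aims 2 and 3.

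Section 6.1 defines the SA1 primary outcome on the same pair, as "improvement in diabetes control on USS+SAP(d) vs. SAP alone as defined by reduced risk for hypoglycemia", measured by CGM time below 70 mg/dL without an increase in HbA1c. The test is described in one line: "Repeated Measures ANOVA with covariate will assess this effect". The general model is a mixed model "including fixed factors following the factorial designs presented in study figure". The text of neither section states the number of repeated measures in the power calculation, the sidedness, or whether period is a factor.

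The phase order is in Sections 1.1 and 3.7. Group A receives SAP, USS+SAP(d), USS+CLC(d), USS+SAP(d). Group B receives USS+SAP(d), USS+CLC(d), USS+SAP(d), SAP.

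On completion, Section 1.5.1 plans enrolment "so that approximately 76 subjects complete the entire study at University of Virginia", with attrition of up to 31%. Section 2.1 says "we expect that approximately 76% in each arm will complete the study (N=64").

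**The concern.** A Cohen f stated for two conditions, combined with a within-subject correlation of 0.4 and alpha of 0.01, requires well over 76 completers for 90% power. The stated number suggests that the software was run for more measurements than the contrast uses. If so, the 90% belongs to an overall test of any difference among phases, while the claim is about a single one-degree-of-freedom comparison.

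A null SA1 result would be read as carrying a 10% risk of missing f = 0.2, when from completers alone the risk is nearer 28–30% with period effects, or about 15% without. Whether period enters the model is worth about 14 points of power, and the text leaves that choice open.

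**Working it through.** **Inputs (Section 6.2):** f = 0.2, alpha = 0.01, rho = 0.4, 76 completers. **Assumed:** two equal sequences (38 completers each), compound symmetry, unit variance, two-sided test, no covariate gain. For two conditions d = 2f = 0.4.

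**1. Reproducing the plan's figure.** Within-factor repeated-measures F test with m measurements: lambda = N·m·f²/(1 − rho), df1 = m − 1, df2 = (N − 2)(m − 1), epsilon = 1.

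| m | lambda at N = 76 | Power at N = 76 | N for 90% |
|---|---|---|---|
| 2 | 76·2·0.04/0.6 = 10.13 | 70.4% | 115 |
| 3 | 15.20 | 82.9% | 90 |
| 4 | 20.27 | 90.9% | 75 |
| 5 | 25.33 | 95.4% | 64 |

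Four measurements match 76, and 76/0.69 = 110.1. This m is inferred, not stated; m = 5 with epsilon = 0.8 also gives 76. Either way the test is an overall one across phases.

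**2. The SA1 contrast with period effects.** SAP occurs only in phase 1 (Group A) and phase 4 (Group B). Phases 2 and 3 set USS+SAP(d) against USS+CLC(d) only. The usable information is therefore each subject's change from phase 1 to phase 4, compared between sequences:

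- Variance of one subject's change: 2(1 − rho) = 1.2.
- The difference in mean change between sequences estimates twice the effect, so the variance of the effect is (1.2/38 + 1.2/38)/4 = 1.2/76 = 0.01579, SE 0.1257.
- Noncentrality: 0.4/0.1257 = 3.18. Power is 70.4% (74 df) to 72.0% (223 df).

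Generalized least squares on the full four-period design gives the same variance. The two extra phases add nothing to this contrast once period is fitted.

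**3. Pooled, no period term.** SAP against the mean of both USS+SAP(d) phases: 1 + (1 + 0.4)/2 − 2(0.4) = 0.9 per subject; 0.9/76 = 0.01184. Power is 84.5% to 85.8%.

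**4. Adding partial data from 34 dropouts (17 per arm, timing assumed).**

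| Dropout timing | Period effects | No period term |
|---|---|---|
| All after phase 3 | 80% | 93% |
| All after phase 2 | 80% | 92% |
| All after phase 1 | 79% | 90% |
| A quarter each after 0, 1, 2, 3 phases | 78% | 90–91% |
| Half before phase 1, rest spread evenly | 76% | 89% |
| All before phase 1 | 72% | 86% |

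If all 110 completed, period effects would give 88–89% and no period term 96–97%.

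**5. Other routes to 90% at 76 completers.**

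- Larger effect, period effects fitted: f = 0.25 gives about 91%.
- Covariate, period effects fitted: removing 20% of within-subject error variance gives 82–83%; about 33–35% must be removed for 90%.
- One-sided alpha of 0.01: 79–80% with period effects; 90% only if also pooled without them.
- SA2 is not affected: f = 0.3 with two conditions gives 98%.

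**6. Section 2.1.** 76/110 = 69.1%, while 0.76 × 110 = 83.6. Neither 76% nor 64 fits 110 randomized and 76 completing. One possible origin is a previous target of 84 (0.76 × 84 = 63.8), and another is the m = 5 row above. The documents do not settle which.

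**The case against.** The software arithmetic is not wrong: four phases are in the design, and four measurements give 90.9% at 76. The planned analysis is an intention-to-treat mixed model, which would use dropouts' data and a covariate, so a completers-only figure understates it. No period term is named in the text, and without one the partial-data figures are 89–93% unless everyone who drops out does so before phase 1. SA1 is directional, and f = 0.2 is a lower bound described as conservative.

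A further point concerns d = 2f. If f = 0.2 were the spread of four phase means with SAP differing from three equal others, d would be 0.46. Power would then be 85–86% with period effects, 94–95% pooled, and about 90% with period effects plus evenly spread dropouts.

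Part of this stands. The defect is a mismatch between the test and the claim, not a slip in the software. The period factor may be shown in the design figure, which was not available for this check. But Section 6.2 defines f on the two-modality comparison, not on four means. The four-mean reading also cuts both ways: if USS+CLC(d) exceeds USS+SAP(d) by half the SA1 effect, d falls to 0.37 and power to 61–63% with period effects, or 76% pooled. Section 6.2 claims no gain from partial data, a covariate or a one-sided test, and an F test has no one-sided form. It states the 90% at the lower bound of f, so a larger true effect does not rescue that statement.

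**Conclusion.** The concern holds. On its own inputs, the plan's 90% belongs to an overall test across about four measurements. For USS+SAP(d) vs SAP, 76 completers give 70–72% with period effects, or about 85% pooled without them. With period effects and no covariate gain, f = 0.2 does not reach 90% under any dropout pattern, since 110 completers give at most 89%. About 90% is reachable only through choices the text does not state: no period term with favourable dropout timing, a one-sided pooled test, or a strong covariate.

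These figures rest on d = 2f, compound symmetry, equal sequences and a two-sided alpha of 0.01. The shortfall concerns SA1, not SA2. The Section 2.1 conflict is a separate, certain inconsistency. This should be fixed, but it does not call the sample size or the conduct of the trial into question.

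**What to change.** Keep 110. In Section 6.2, name the test, the number of measurements, the sidedness, the SA1 contrast and the handling of period, and replace the 90% with the power for that contrast. Suggested text:

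> With 76 completers, f = 0.2, correlation 0.4 and two-sided alpha = 0.01, power for USS+SAP(d) vs SAP is about 70–72% with period effects in the model (about 85% if both USS+SAP(d) phases are pooled without period effects), and about 90% at f = 0.25, before any gain from covariates or partial data.

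If a gain from partial data or the covariate is to be claimed, state the assumed dropout timing or variance reduction and recompute. In Section 2.1, replace the completion figures with those of Sections 1.5.1 and 6.2 (about 69%, 76 completers).

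The cost is wording in two sections and no extra patients. The stated power becomes less favourable, and the treatment of period must be fixed in advance.
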